1.1 Protocol Amendment: Summary of Changes

Previous Protocol Versions

Protocol	Date
Original	04 February 2016
Amendment 1	05 May 2016
Amendment 2	30 November 2016

The purpose of this amendment is to:

- Section 1.2, Add the planned number of sites for this study of 56.
Rationale: Clarify number of sites in the study.
- Section 8.1.4.1, Add that the 95% confidence intervals of treatment difference will also be provided.
Rationale: The protocol was updated to include clarifications requested by regulatory Authorities.
- Section 8.1.4.1, Add a sensitivity analysis controlling for change from baseline in body weight using logistic regression models, for the primary efficacy endpoint. Analysis details will be specified in the SAP prior to study unblinding and prior to database lock.
Rationale: The protocol was updated to include clarifications requested by regulatory Authorities.
- Update Study Designated Physician in Section 1.0 and Section 6.1.5
Rationale: Update information from Administrative Change 1.
- Update Alternate Contact in Section 7.0
Rationale: Update information from Administrative Change 1.
- Update List of Protocol Signatories in Appendix B
Rationale: Update information from Administrative Change 1.

An itemized list of all changes made to this protocol amendment can be found in [Appendix S](#).

1.2 Synopsis

AbbVie Inc.	Protocol Number: M15-574
Name of Study Drug: Adalimumab	Phase of Development: 4
Name of Active Ingredient: Adalimumab	Date of Protocol Synopsis: 13 December 2017
Protocol Title: A Phase 4, Double-Blind, Randomized, Placebo-Controlled, Multicenter Study to Assess the Safety and Efficacy of Adalimumab used in Conjunction with Surgery in Subjects with Moderate to Severe Hidradenitis Suppurativa	
Objective: Assess the safety and efficacy of adalimumab prior to surgery in subjects with moderate to severe Hidradenitis Suppurativa (HS) who are surgical candidates.	
Investigators: Multicenter	
Study Sites: The planned number of sites for this study is 56.	
Study Population: Male or female subjects between the ages of 18 and 65, inclusive, with moderate to severe HS having 
 • at least 3 distinct anatomical regions involved with inflammatory HS lesions; • either one axilla or one inguinal region that requires excisional surgery with healing by secondary intention, and containing at least one active HS lesion; and • the non-surgical HS sites must have a total AN count ≥ 3, with at least one of these sites rated Hurley Stage II or III. 	
Number of Subjects to be Enrolled: 200 The study is designed to enroll approximately 200 subjects. Assuming the true treatment difference in this study population is at least 20%, 100 subjects per arm will provide at least 80% power to detect the treatment difference at the alpha level of 0.05. The study also has at least 80% power to demonstrate the point estimate of the treatment difference of at least 15%. The response rates observed in combined PIONEER I and II studies (Studies M11-313 and M11-810) for the Hidradenitis Suppurativa Clinical Response (HiSCR, defined as at least a 50% reduction in the HS abscess plus inflammatory nodule [AN] count with no increase in abscess count and no increase in draining fistula count relative to Baseline) at Week 12 were 50.6% and 26.8% in the adalimumab every week group and placebo group, respectively. Due to the potential differences between the population of moderate-to-severe HS patients who are surgical candidates and the general moderate-to-severe HS patient population, a conservative estimate of 20% treatment difference is used for the power calculation.	
Methodology: This double-blind, placebo-controlled study consists of a 7 – 30-day Screening Period followed by 24-weeks of active treatment. The eligible subject must have a requirement for surgery of HS lesions in a single axilla or unilateral inguinal region. Subjects will be randomised 1:1 with stratification for Hurley Stage (II versus III worst stage across all body regions) and anatomical location of the planned surgery for HS lesions (axilla versus inguinal region). Study drug treatment will follow the approved dosage for HS, including loading doses at the beginning of the 12-week pre-surgery period (Period A), followed by a 2-week peri-surgery period (Period B) with surgery scheduled for Week 13 and a 10-week post-surgery period (Period C).	

Methodology (Continued):

Study visits will occur as follows:

- Period A (pre-surgery) study visits will occur at Day 1 (Week 0) and Weeks 2, 4, 8, and 12.
- Period B (peri-surgery) the subject will be under the care of the designated surgeon.
- Period C (post-surgery) study visits will occur at Weeks 15, 17, 20, and 24.

Evaluation for safety and efficacy throughout the 24-week study period will include

- 1) clinical observations of the HS lesions (both in the planned surgical site and at least two other distinct anatomical regions with HS lesions),
- 2) laboratory measurements of serum and plasma samples, and
- 3) patient reported outcomes (PROs).

Optional participation in exploratory research and validation studies will include the collection of serum and plasma samples, and tissue samples (both of non-lesional skin and HS lesional skin, specifically at the planned surgical site) at specified various time points throughout the study.

In selected study sites Doppler ultrasound and digital imaging may be performed with optional participation by the study subject.

Diagnosis and Main Criteria for Inclusion/Exclusion:

Main Inclusion:

1. Male and female subjects between the ages of 18 and 65, inclusive;
2. Subject must have a skin lesions that are diagnostic of HS for at least 1 year (365 days) prior to the Baseline visit;
3. Subject must have at least 3 distinct anatomical regions involved with inflammatory (also termed 'active') HS lesions; including
 - a. either an axilla or unilateral inguinal region (limited to the inguino-crural fold and adjacent areas that requires excisional surgery (hereinafter designated the 'HS surgical site'), and
 - b. with at least one of the other affected HS regions (e.g., contralateral axilla, contralateral inguinal region, buttocks, inframammary region; hereinafter designated the 'HS non-surgical sites') rated as Hurley Stage II or III;
4. Subject must have a total abscess and inflammatory nodule (AN) count of greater than or equal to 3 at the Baseline visit within the HS non-surgical sites;
5. The HS surgical site must contain at least one active HS lesion;
6. The HS surgical site must require excisional surgery and is large enough to require healing by secondary intention as assessed by the designated surgeon;

Diagnosis and Main Criteria for Inclusion/Exclusion (Continued):

Main Inclusion (Continued):

7. If female subject, is either
- not of childbearing potential, defined as
 - postmenopausal for at least 1 year (365 days) or
 - surgically sterile (bilateral tubal ligation, bilateral oophorectomy, and/or hysterectomy);
 - of childbearing potential and is practicing an approved method of birth control throughout the study and for 150 days after last dose of study drug.

Examples of approved methods of birth control include the following (see local informed consent for more detail):

- Intrauterine device (IUD) or Intrauterine hormone-releasing system (IUS); or
 - Hormonal contraceptives at least 30 days prior to study drug administration; and/or
 - A vasectomized partner; and/or
 - True abstinence.
8. Females of childbearing potential must have a negative serum pregnancy test result (conducted at the central lab) at Screening and a negative urine pregnancy test (conducted at the site) at Day 1;
- Females of non-childbearing potential (either postmenopausal or permanently surgically sterile as defined above) at Screening do not require pregnancy testing.
9. Subject must agree to daily use of one of the following over-the-counter topical antiseptics on their HS lesions (excepting the post-surgical wound): chlorhexidine gluconate, triclosan, benzoyl peroxide, or dilute bleach with shower or bath throughout the entirety of the study;
10. Subject has a negative tuberculosis (TB) screening assessment (see test to be performed in paragraph below) and negative chest x-ray (CXR) (posterior anterior and lateral view) at Screening. If the subject has evidence of a latent TB infection; the subject must initiate and complete a minimum of 12 weeks (or per local guidelines, whichever is longer) of an ongoing TB prophylaxis or have documented completion of a minimum of 4 weeks of TB prophylaxis prior to the Baseline visit and should be evaluated by a physician experienced in the evaluation and treatment of TB patients before entering the trial;
- In patients treated with corticosteroids (equivalent to Prednisone 5 mg or above – with ongoing treatment or treatment within 1 month prior to TB screening), TB screening must be performed using a QuantiFERON-TB Gold In-tube test or equivalent.
 - In patients NOT treated with corticosteroids (equivalent to Prednisone 5 mg or above – with ongoing treatment or treatment within 1 month prior to TB screening), PPD or QuantiFERON-TB tests may be used.
11. Subject is judged to be in good general health, as determined by the Study Investigator based upon the results of a medical history, physical examination, laboratory profile, CXR and a 12-lead electrocardiogram (ECG) performed during the Screening period and confirmed at the Baseline visit;
12. Subject must be able and willing to self-administer subcutaneous (SC) injections or have a qualified person available to administer SC injections; and
13. Subject must be able and willing to provide written informed consent and comply with the requirements of this study protocol.

Diagnosis and Main Criteria for Inclusion/Exclusion (Continued):

Main Exclusion:

1. Subject has a draining fistula count of greater than 20 at the Baseline visit;
2. Subject requires surgery at any anatomical site other than an unilateral axilla or inguinal region site;
3. Subject requires surgical management prior to Week 13; based on the designated surgeon's assessment;
4. Subject requires, based on the designated surgeon's assessment, excisional surgery with primary closure, partial surgical reduction of the excised area with surgical suture, or reconstruction techniques as the method of closure being most beneficial for the subject;
5. Subject has any other active skin disease or condition (e.g., bacterial, fungal or viral infection) that may interfere with assessment of HS;
6. Subject is taking high-dose systemic corticosteroids at the Baseline visit (see Section 5.2.3.3), or has taken high-dose systemic corticosteroids (see Section 5.2.3.3) within five half-lives of that specific corticosteroid prior to the Baseline visit;
7. Subject received biologic therapies with potential therapeutic impact for HS less than 6 months (178 days) prior to the Baseline visit;
8. Subject received prescription topical therapies (excluding over-the-counter topical antiseptics) for the treatment of HS within 14 days prior to the Baseline visit;
9. Subject received systemic clindamycin or rifampin within 28 days prior to the Baseline visit;
10. Infection(s) requiring treatment with intravenous (IV) anti-infectives (antibiotics, antivirals, antifungals) within 30 days prior to the Baseline visit, except as required as part of an anti-TB regimen;
11. Prior exposure to biologics that have a potential or known association with progressive multifocal leukoencephalopathy (PML i.e., natalizumab or rituximab);
12. Subject has been treated with any investigational drug of chemical nature within a minimum of 30 days or five half-lives (whichever is longer) of the drug prior to the Baseline visit;
13. Known hypersensitivity to adalimumab or its excipients;
14. History of demyelinating disease (including myelitis) or neurologic symptoms suggestive of demyelinating disease;
15. Subject has suspicion of sepsis, cytomegalovirus infection, listeriosis or other opportunistic infections, or has history of invasive infection (e.g., listeriosis, histoplasmosis), human immunodeficiency virus (HIV);
16. Subject has an active systemic viral infection or any active viral infection that based on the Study Investigator's clinical assessment make the subject an unsuitable candidate for the study;
17. Hepatitis B: HBsAg positive (+) or detected sensitivity on the HBV-DNA PCR qualitative test for HBcAb/HBsAb positive subjects;
18. Chronic recurring infections or active TB;
19. History of moderate to severe congestive heart failure (NYHA class III or IV), recent cerebrovascular accident, interstitial lung disease (ILD) and any other condition which, in the opinion of the investigator, would put the subject at risk by participation in the protocol;
20. Evidence of dysplasia or history of malignancy (including lymphoma and leukemia) other than a successfully treated non-metastatic cutaneous squamous cell carcinoma, basal cell carcinoma or localized carcinoma in situ of the cervix;

Diagnosis and Main Criteria for Inclusion/Exclusion (Continued):

Main Exclusion (Continued):

21. Females who are breastfeeding or considering becoming pregnant during the study and during the 5 months following the last dose of adalimumab;
22. History of clinically significant drug or alcohol abuse in the previous 12 months;
23. Clinically significant abnormal screening laboratory results as evaluated by the Investigator; and
24. Subject is considered by the Study Investigator, for any reason, to be an unsuitable candidate for the study.

Active Study Drug: Adalimumab
Doses: 160 mg/3.2 mL Day 1 (Week 0), 80 mg/1.6 mL Day 15 (Week 2) and 40 mg/0.8 mL every week from Week 4 to Week 23.
Mode of Administration: Subcutaneously (SC)

Reference Therapy: Placebo
Doses: 3.2 mL Day 1 (Week 0), 1.6 mL Day 15 (Week 2), and 0.8 mL every week from Week 4 to Week 23.
Mode of Administration: Subcutaneously (SC)

Duration of Treatment: 23 weeks

Criteria for Evaluation:

Efficacy:

The primary efficacy variable is the proportion of subjects achieving HiSCR at Week 12. The secondary endpoints include the proportion of subjects achieving HiSCR-es (defined as the HiSCR excluding the HS surgical site) at Weeks 12 and 24, the change in surface area of the HS surgical site at Week 12, and the proportion of subjects at Week 12 that require less extensive surgery than the surgical plan (determined at Baseline) or no surgery. Other parameters will be collected and may be analysed, including C-reactive protein (CRP), active HS lesion count, and patient reported outcomes (PROs).

Pharmacokinetic:

Blood samples will be collected for the measurement of serum adalimumab concentrations at Baseline and Weeks 4, 8, 12, 15, 17, 20, 24/Premature Discontinuation visit if the subject discontinues prior to Week 24. Blood samples will be collected for the measurement of anti-adalimumab antibody (AAA) at Baseline, and Weeks 4, 8, 12, 15, 20, and 24/Premature Discontinuation visit if the subject discontinues prior to Week 24.

Safety:

Adverse events, adverse events of special interest and adverse events concerning the surgical site, laboratory data and vital signs will be assessed throughout the study.

Exploratory Research Variables and Validation Studies (Optional):

Prognostic, predictive, and pharmacodynamic biomarker signatures may be investigated. Samples for different applications including, but not limited to, pharmacogenetic, epigenetic, transcriptomic, proteomic, and targeted investigations will be collected at various time points.

Statistical Methods:

Efficacy:

The primary analysis will be the comparison of the adalimumab treatment group versus the placebo treatment group in the proportion of subjects achieving HiSCR at Week 12.

Ranked secondary endpoints with comparison of the adalimumab treatment group versus the placebo treatment group include:

1. Proportion of subjects achieving HiSCR-es (HiSCR evaluation excluding the HS surgical site) at Week 12;
2. Proportion of subjects achieving HiSCR-es at Week 24;
3. Percent change in surface area of the planned surgical site from Baseline to Week 12; and
4. Proportion of subjects that require a less extensive surgery than the surgical plan documented at Baseline, or no longer require surgery as determined by the designated surgeon.

Other efficacy endpoints for which data will be collected and may be analysed include:

1. C-reactive protein (CRP) and white cell count;
2. PROs including DLQI, EQ5D™, HS-PGA-SP, HS-PGIC, HSIA, HSSA, SF-12, TSQM (treatment efficacy subscale), and WPAI:SHP;
3. Proportion of subjects that experience a flare of active HS lesions, during Period A and during the study; and
4. Proportion of subjects that experience at least 25% increase in each lesion type relative to Baseline at each study visit, during Period A and during the study.

The primary efficacy analysis will be carried out in the Intent-to-Treat (ITT) Population in the Period A, defined as all patients who are randomised at the Baseline visit. Treatment difference in response rates between adalimumab and placebo will be conducted by Cochran-Mantel-Haenszel (CMH) test, stratified by the stratification factors used for randomisation. All other secondary efficacy variables in Period A will be analysed by ANCOVA (for continuous variables) with treatment, baseline value and stratification factors in the model, or by CMH (categorical variables) adjusting for stratification factors.

Non-responder imputation will be used as the primary approach to impute the missing values with last-observation-carried-forward and Multiple Imputation as sensitivity analyses for the primary endpoint.

Pharmacokinetic:

Adalimumab trough serum concentrations will be summarized at each time point using descriptive statistics. In addition, pharmacokinetic-pharmacodynamic (PK-PD) model-based analyses will be performed to evaluate adalimumab PK and exposure-response relationships.

Statistical Methods (Continued):

Safety:

All adverse events (AE), serious adverse events (SAE), AEs leading to discontinuation, and pre-specified AEs of special interest and adverse events concerning the surgical site will be collected during the study and up to approximately 70 days after the last dose of study drug, for subjects who do not elect to treat his/her HS disease with commercial adalimumab.

Safety analyses will be carried out using the Safety Population, which consists of subjects who received at least one dose of study drug. Pretreatment AEs will be summarized. A treatment-emergent AE (TEAE) is defined as an event with onset or worsening after the first study drug injection and within approximately 70 days after the last study drug injection, for subjects who do not elect to treat his/her HS disease with commercial adalimumab.

The number and percent of subjects experiencing TEAEs will be tabulated using the Medical Dictionary for Drug Regulatory Activities (MedDRA[®]) system organ class and preferred term. Comparisons of the percentages of subjects experiencing an AE in the adalimumab group versus the placebo group will be performed using Fisher's exact test for data collected in the entire study, and separately for Period A, Period B, and Period C. Summaries (including percentages and event per 100 patient-years) of SAEs, deaths, AEs leading to discontinuation from the study, and pre-specified AEs of special interest will be provided as well. Mean change in laboratory variables and vital sign variables at each visit will be summarized; the comparison between the adalimumab treatment group and placebo group will be carried out using a one-way ANOVA.

Immunogenicity:

Anti-Adalimumab Antibody (AAA) will be evaluated for each subject and rates of AAA positive will be calculated. As appropriate, the effect on adalimumab PK, efficacy, and treatment-emergent adverse events may be evaluated.

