8.0 Statistical Methods and Determination of Sample Size

8.1 Statistical and Analytical Plans

The objectives of the statistical analyses are to evaluate the clinical safety and efficacy of adalimumab compared to placebo in subjects with moderate to severe HS who are scheduled to undergo excisional surgery for the 12-week period prior to surgery (Period A), the 2-week perioperative period (Period B) and during a 10-week post-surgical period (Period C). Complete, specific details of the statistical analysis will be described and fully documented in the Statistical Analysis Plan (SAP). The SAP will be finalized prior to the database lock and blind break.

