### 6.0 Efficacy Analysis

#### 6.1 General Considerations

[figure not shown]
The efficacy analysis will be conducted among the ITT Population. A sensitivity analysis for the primary efficacy endpoint may also be conducted among the Per-protocol Population, if defined.

Categorical variables will be analysed using Cochran-Mantel-Haenszel (CMH) test, stratified by baseline Hurley Stage and anatomical location of the surgical. Continuous variables will be analysed using ANCOVA method, with treatment, baseline Hurley Stage, anatomical location of the surgical, and Baseline values in the model.

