### 7.2 Analysis of Adverse Events

Treatment-emergent adverse events (TEAEs) are defined as any event with an onset that is after the first dose of study drug and with an onset date within 70 days after the last dose of study drug in the analysis period, or prior to the first dose in the subsequent period for subjects who entered in to the subsequent period.

Pre-treatment AEs will be summarized separately.

All TEAEs, serious adverse events (SAEs), AEs leading to discontinuation and AEs of Safety Interest will be summarized. The number and percentages of subjects experiencing TEAE will be tabulated using the Medical Dictionary for Drug Regulatory Activities (MedDRA®) system organ class and preferred term.

Summaries (including percentages and event per 100 patient-year) of SAEs, deaths, AEs leading to discontinuation, and AEs of Special Interest will be provided as well. No statistical tests will be performed.

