### 7.3 Analysis of Laboratory Data

Mean change from Baseline in laboratory variables will be summarized. Shift tables for changes from Baseline according to the normal range will be provided. Frequencies and percentages of subjects with post baseline values meeting Criteria for Potentially Clinically Significant Laboratory values (i.e., the Common Toxicity Criteria (CTC) of Grade 3 or higher, as well as being a higher grade than the baseline CTC grade) will be summarized. For the assessments of laboratory data, values observed more than 70 days after the last dose of study drug will be excluded.

[figure not shown]

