### 7.4 Analysis for Vital Signs

Changes from Baseline to post-baseline visits will be summarized. The number and percentage of subjects meeting the criteria for potentially clinically significant vital sign values will be summarized.

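### The protocol synopsis compares laboratory and vital-sign changes by a one-way ANOVA without baseline as a covariate, and the SAP neither adopts nor withdraws that comparison

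*Protocol*

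**What the plan says.** The safety part of the protocol synopsis (1.2, Statistical Methods) first says "Mean change in laboratory variables and vital sign variables at each visit will be summarized". It then adds that "the comparison between the adalimumab treatment group and placebo group will be carried out using a one-way ANOVA". The protocol's full safety section, 8.1.5, does not repeat this comparison. Protocol 8.1 leaves the complete analysis details to the SAP.

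For laboratory data, SAP 7.3 says "Mean change from Baseline in laboratory variables will be summarized", and adds shift tables and counts of potentially clinically significant values. For vital signs, SAP 7.4 says "Changes from Baseline to post-baseline visits will be summarized", again with counts of potentially clinically significant values. Neither section names a between-arm comparison. The sentence "No statistical tests will be performed" does appear in the SAP, but it closes 7.2, the adverse-event section.

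Continuous efficacy variables are treated differently. The synopsis has the secondary ones in Period A "analysed by ANCOVA (for continuous variables) with treatment, baseline value and stratification factors in the model". SAP 6.1 gives the general rule as "Continuous variables will be analysed using ANCOVA method, with treatment, baseline Hurley Stage", and goes on to add surgical location and the baseline value.

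**The concern.** A one-way ANOVA of change has treatment as its only term. The baseline value is subtracted from each follow-up value but is not a covariate, so the regression of change on baseline stays in the error term. The same documents use the more precise model for continuous efficacy variables and give no reason for a different one here. Baseline values and both stratification factors are already collected, so the better model needs no new data.

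There is also a gap between the two documents. The synopsis announces a comparison that SAP 7.3 and 7.4 leave open. An analyst could follow the synopsis and produce ANOVA p-values, or follow the SAP and produce none. CRP shows the difficulty: hsCRP is listed in the protocol's clinical laboratory table, and change in CRP is also an unranked efficacy variable. On a literal reading, the same change falls under both ANOVA and ANCOVA.

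What is at stake is the precision of the safety estimates, and clarity about which analysis will be reported.

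**Working it through.** **Is there a plan figure to reproduce?** No. The documents give no SD, correlation, effect size or power for any laboratory or vital-sign variable. Their power statement concerns HiSCR only.

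**Inputs**
- Planned n = 100 per arm, allocated 1:1 (protocol 8.2 and 8.3).
- Outcome: change from Baseline at a visit (synopsis).
- Assumed: equal SD at baseline and follow-up, set to 1, and baseline to follow-up correlation rho of 0.3, 0.5, 0.7 or 0.9.

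**Formulas**
- Change-score ANOVA: variance per subject 2(1 - rho), so SE = sqrt[2(1 - rho) x 2/n].
- ANCOVA with baseline: residual variance 1 - rho^2, so SE = sqrt[(1 - rho^2) x 2/n].
- Variance ratio, ANCOVA to ANOVA: (1 - rho^2) / [2(1 - rho)] = (1 + rho)/2.
- Excess interval width of ANOVA: sqrt[2/(1 + rho)] - 1.
- Shift of the ANOVA estimate for a chance baseline difference b: rho x b - b = -(1 - rho) x b, here with b = 0.2 SD.

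**Worked case, rho = 0.5.** ANOVA: sqrt(1.00 x 0.02) = 0.141. ANCOVA: sqrt(0.75 x 0.02) = 0.122. Excess width: sqrt(2/1.5) - 1 = 15%. Shift: -0.5 x 0.2 = -0.10 SD.

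| rho | SE, ANOVA of change | SE, ANCOVA | Variance ratio | ANOVA interval wider by | Shift for 0.2 SD imbalance |
|---|---|---|---|---|---|
| 0.3 | 0.167 | 0.135 | 0.65 | 24% | -0.14 SD |
| 0.5 | 0.141 | 0.122 | 0.75 | 15% | -0.10 SD |
| 0.7 | 0.110 | 0.101 | 0.85 | 8% | -0.06 SD |
| 0.9 | 0.063 | 0.062 | 0.95 | 3% | -0.02 SD |

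**The last two columns are one loss, not two.** The ANOVA variance splits as 2(1 - rho) = (1 - rho^2) + (1 - rho)^2. The second term is the variance contributed by chance baseline imbalance. At rho = 0.5 this is 1.00 = 0.75 + 0.25. The ANOVA standard error therefore already allows for the shift on average.

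**Simulation check.** With 4,000 simulated trials per setting, 100 per arm and no treatment effect, both estimators averaged about 0. The SDs of the estimates, ANOVA then ANCOVA, were 0.141 and 0.123 (rho 0.5), 0.110 and 0.102 (rho 0.7), and 0.063 and 0.061 (rho 0.9). These agree with the formulas.

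**Strata.** The further gain from Hurley stage and surgical location cannot be computed, because the documents do not say how strongly either predicts any laboratory or vital-sign value.

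**The case against.** The strongest reply is that the analysis criticised may never be run. The ANOVA sentence stands only in the synopsis, dated 13 December 2017. The protocol leaves the details to the SAP, and SAP version 3.0, dated 12 August 2019, plans descriptive summaries. The SAP also turns away from tests for adverse events, where the protocol had planned Fisher's exact test. All this makes a descriptive intent plausible, and for that reason the fix offers a descriptive option. It does not settle the matter: the no-tests sentence is confined to adverse events, 7.3 and 7.4 have no counterpart, and the SAP refers further conventions to a supplement that is not among the documents.

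A reader might infer from the SAP's summary of changes that the ANOVA survives, since its removal is not listed. That inference fails, because the list tracks changes between SAP versions and not departures from the protocol.

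A reader might also infer that the ANOVA ignores baseline or gives biased results. It does neither. The outcome is a change, so baseline is subtracted. Under randomisation the estimate is unbiased and the type I error is valid.

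Finally, the size rests on an assumed correlation and is small when that correlation is high. This stands. It is why a range is shown and why no power figure is offered: the plan gives no laboratory or vital-sign effect for which to compute one.

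**Conclusion.** The point holds as a modest matter of precision and consistency. The only between-arm method that the documents name for laboratory and vital-sign changes is a treatment-only ANOVA in the synopsis, and the SAP leaves its status open. If that comparison is run, its intervals are about 3% to 24% wider than those of a baseline-adjusted ANCOVA over correlations from 0.9 to 0.3, assuming equal SDs and 100 subjects per arm. The percentages do not depend on n; the standard errors do.

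A reader might go further and conclude that the trial's safety or efficacy findings would be unsound. The documents do not support that. These are unranked safety data outside the testing hierarchy, no primary or ranked endpoint uses this model, and the ANOVA is a valid method. The case for change is that the gain in precision is almost free and that the two documents should agree.

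**What to change.** Choose one of two courses and state it in both documents.

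1. **Keep the comparison.** In the synopsis safety paragraph, replace the one-way ANOVA with an ANCOVA of change from Baseline at each visit, with treatment, baseline value, Hurley stage and surgical location as terms (the SAP 6.1 model). Add the same sentence to SAP 7.3 and 7.4, which at present name no method. Report the adjusted adalimumab minus placebo difference with its 95% CI. State which sample is the baseline when laboratory tests are not repeated on Day 1, since the notes to Appendix C allow Screening results to stand when Screening was 14 days earlier or less.

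2. **Descriptive only.** Delete the ANOVA sentence from the synopsis, and add a line to SAP 7.3 and 7.4 that no between-arm tests will be made.

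The first course costs a few sentences and one model per variable and visit, with no new data. Its drawback is extra output: Table 1 of the protocol lists 11 haematology and 18 chemistry variables, 29 in all, before vital signs. The second course costs only the edits.
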